#### **15.4 Strategy for analysis of subgroup heterogeneity of treatment effects (HTE)**

While a head to head drug comparison is not the primary goal of this study, we will take the opportunity to examine similarities and differences between the treatment regimens using causal inference methods (described in section 15.10). Fitted models will provide parameter estimates that will be used to obtain point estimates, confidence intervals (CI) and hypothesis tests to characterize and compare treatment regimens within each subgroup. For each outcome variable these auxiliary comparisons of regimens will include an equivalence test procedure as well as a superiority test procedure. The subgroup-specific treatment effects will be compared to evaluate evidence of HTE. For purposes of hypothesis generation and not testing, exploratory analyses of HTE for other subgroups will be performed; e.g., such as medication adherence rates among subgroups with mental health issues or drug and alcohol use (MH/SA Hx), or other groups that may be suggested by the data. Hypotheses will be generated but not tested.

#### **15.5 Overview of Plans for Manuscript #1: Change in Treatment Side Effects from T1 to T2/T3**

The primary analyses for manuscript #1 will rely on a linear model for change from baseline for each PRO variable conditional on baseline covariates which include *cirrhosis status, age, race, sex at birth, treatment regimen, cirrhosis-by-regimen interaction*, and the *baseline PRO score*. Inclusion of the baseline PRO score as a covariate has several advantages for clarity of interpretation and improved precision of estimators of interest. The analysis will focus on point estimates and confidence intervals.

PRO variables of interest in manuscript #1 are described here by aim:

Aim 1a, MSAS. The outcome variable will be change from baseline (T1) to the larger of the two MSAS scores (T2 and T3) during treatment. As an aid to interpretation, additional supportive tabulations for each of the 32 side effects will be examined; e.g., the incidence of new side effects and the exacerbation of existing symptoms during treatment will be characterized in regard to the raw frequency, severity and distress items.

Aim 1b, PROMIS®. The primary analyses will focus on 6 side effect-specific PROMIS® T-scores and 1 HIT headache score. The outcome variable will be change from baseline (T1) to the larger of the two T-scores (T2 and T3) during treatment. As an aid to interpretation of the main results, additional supportive tabulations for specific survey items will be examined.

Aim 1c, HCV-PRO. In the primary analysis, the outcome variable will be change from baseline to the larger of the two HCV-PRO scores (T2 and T3) during treatment.

Aim 1d, Pre-existing medical conditions. For each of several selected pre-existing condition at baseline, we will descriptively examine which conditions stay the same, get worse, or get better, during HCV treatment.

Aim 1e, OOP Costs. This outcome variable will be patient-reported cumulative (T2-T4) direct costs and indirect costs on  $\log_{10}$  scale. Sensitivity analyses will include use of a generalized log-linear model. Treatment differences in OOP costs could affect adherence and / or persistence and hence impact SVR. The co-variation of OOP costs with other outcomes will be explored in order to generate new hypotheses about the role of OOP costs.

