#### 14.4 HCV-PRO to measure well-being and functioning (Aim 1c, 3b, 4d)

The HCV-PRO is a newly developed survey designed to assess the well-being and functional status of patients with HCV. It was developed in accordance with the PRO guidelines issued by the US FDA and demonstrated good reliability and convergent validity was moderate-high ( $r > 0.50$ ). HCV-PRO items measure physical, emotional and social functioning, productivity, intimacy, and perception of quality of life. Participants select responses from a 5-point Likert scale: 1=“all of the time” to 5=“none of the time”. A higher total score indicates higher functioning.

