### **15 STATISTICAL ANALYSIS STRATEGY**

#### **15.1 Analysis plans registered in the master protocol document**

To help ensure reproducible results, these *a priori* plans specify detailed steps for the major inferential analyses along with guidelines for sensitivity analyses performed to assess the robustness of the major results to reasonable perturbations of the *a priori* assumptions, choices, and methods used. The plans also include (1) use of supportive analyses of subscales as an aid for understanding and interpreting the major analysis results, (2) a role for outcome-dependent exploratory analyses for hypothesis generation / refinement, and (3) necessary descriptive graphical and tabular methods used to characterize the participants, visualize the data and examine relationships among variables.

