#### **15.3 Supportive longitudinal analysis and interpretation of changes from baseline**

HCV-related symptom scores will be measured longitudinally. As an aid to interpretation of the primary results, and for purposes of generating new hypotheses, auxiliary longitudinal analyses of these repeated measures may also be explored.

Any increments from Baseline (T1) during treatment (T2/T3) will represent worsening of HCV-related symptoms or commencement of new onset treatment side effects. Similarly, decrements from Treatment (T2/T3) to 12-weeks post-treatment (T4) will represent amelioration or disappearance of symptoms. For any

symptoms remaining at T4, decrements from T4 to T5 will represent further healing. Thus for each individual the longitudinal trajectories of the scores represents that individual's history of waxing and/or waning of HCV-related symptoms. Secondarily, complementary analyses of each of the 32 symptoms will be used to investigate whether side effects that begin during treatment tend to resolve and to investigate the incidence of new symptoms or side effects that appear after treatment ends.

Treatment-related side-effects scores will also be measured longitudinally. Ideally, any increment from T1 to T2/T3 will be completely reversed by a decrement from T2/T3 to T4 or T5. Thus for each individual, the longitudinal trajectories of the scores represents that individual's history of waxing and/or waning treatment-related side-effects and HCV-related symptoms. These trajectories will be summarized descriptively via estimates of occasion-specific mean levels (with confidence intervals) and in terms of patterns of the trajectories represented, for example, by the proportion of patients for whom all treatment-related side-effects disappeared by T4/T5.

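### Taking the larger of the T2 and T3 scores hides loss of function on HCV-PRO and builds a positive change into MSAS and PROMIS

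*Combined protocol and SAP*

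**What the plan says.** Section 15.5 fits a linear model for change from baseline, adjusted for the baseline score and other covariates, and reports point estimates and intervals. The outcomes are:

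- Aim 1a, MSAS: "The outcome variable will be change from baseline (T1) to the larger of the two MSAS scores (T2 and T3) during treatment".
- Aim 1b, PROMIS: "The outcome variable will be change from baseline (T1) to the larger of the two T-scores (T2 and T3) during treatment". The same aim also lists headache: "The primary analyses will focus on 6 side effect-specific PROMIS® T-scores and 1 HIT headache score".
- Aim 1c, HCV-PRO: "the outcome variable will be change from baseline to the larger of the two HCV-PRO scores (T2 and T3) during treatment".

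Section 14.4 gives the direction of HCV-PRO: "A higher total score indicates higher functioning". Aim 1 (section 3.1) is about the harms of each regimen.

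Three places show how the change will be read. Section 15.3 says: "Any increments from Baseline (T1) during treatment (T2/T3) will represent worsening of HCV-related symptoms or commencement of new onset treatment side effects". Section 15.12 sets the precision of mean change beside important differences of 0.10 (MSAS), 3 (PROMIS) and 10 (HCV-PRO). The sample-size appendix, section 2, lists a test of zero mean change for manuscript 1 on all three measures.

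**The concern.** There are two faults.

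**Direction.** On MSAS and PROMIS the larger score is the worse visit. On HCV-PRO it is the better one, so the rule discards the visit at which function was lower. No section reverse-scores HCV-PRO.

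**Reference value.** One baseline score is compared with the higher of two later scores. Scores vary from visit to visit, so the higher of two lies above a single score on average even if treatment does nothing to the mean. On the symptom scales this looks like harm. Adjusting for baseline does not remove it, because it is a shift in the mean of the outcome.

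Aim 1 describes each regimen separately, so an offset common to all regimens stays in every estimate. One paper could report symptom worsening where the means did not move and miss a real loss of function in the same patients.

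**Working it through.** **Inputs** (sample-size appendix, section 2). SD: MSAS 0.6 (range 0.45 to 0.75), PROMIS 10 (6 to 12), HCV-PRO 25.92 (23.641 to 28.835). Important differences: 0.10, 3 and 10. The appendix gives a serial correlation of 0.50 without naming the visits. R below is the T2–T3 correlation; it is an assumption, shown from 0.5 to 0.9.

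**1. The plan's own figures.** The SD of a single-visit change is SD × √(2(1 − 0.50)) = SD. The half-width met with 80% chance is t(0.975, N−1) × SD × √(χ²(0.80, N−1)/(N−1)) / √N. At N = 80 this gives 0.142 / 2.367 / 6.134 for MSAS / PROMIS / HCV-PRO, against the printed 0.14 / 2.37 / 6.14. The tables therefore reproduce for a change to one visit, not to the larger of two.

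**2. Identity.** max(a, b) = (a + b)/2 + |a − b|/2. The expected outcome is the average T2/T3 change plus half the mean |T2 − T3|. This holds for any distribution, and the extra term is zero only if the two visits always agree.

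**3. HCV-PRO direction, no correlation needed.** The expected larger score is never below the larger visit mean. If the true mean change is −10 at one visit and 0 at the other, the planned outcome has expectation 0 or above.

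For its size with normal scores: E[max] = m₁Φ(d) + m₂Φ(−d) + τφ(d), with τ = SD√(2(1 − R)) and d = (m₁ − m₂)/τ. At R = 0.5, τ = 25.92 and d = 10/25.92 = 0.386, so E = −10 × 0.350 + 25.92 × 0.370 = +6.1.

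**4. Offset with no shift.** For equal visit means and SDs, offset = SD × √((1 − R)/π). PROMIS at R = 0.5: 10 × √(0.5/π) = 3.99. A 10-point HCV-PRO loss at both visits appears as −10 plus the HCV-PRO offset.

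| | R = 0.5 | 0.7 | 0.8 | 0.9 |
|---|---|---|---|---|
| MSAS offset (0.10 important) | 0.24 | 0.19 | 0.15 | 0.11 |
| PROMIS offset (3) | 4.0 | 3.1 | 2.5 | 1.8 |
| HCV-PRO offset (10) | 10.3 | 8.0 | 6.5 | 4.6 |
| HCV-PRO, true −10 at one visit, 0 at the other | +6.1 | +4.0 | +2.7 | +1.2 |
| HCV-PRO, true −10 at both visits | +0.3 | −2.0 | −3.5 | −5.4 |

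The offset equals the important difference at R = 1 − π(important difference/SD)², which is about 0.91 (MSAS), 0.72 (PROMIS) and 0.53 (HCV-PRO). Over the plan's SD ranges this runs from 0.84 to 0.94, 0.21 to 0.80 and 0.44 to 0.62.

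**5. What shrinks it.**
- Unequal visit means. With the visits one important difference apart, the excess over the higher visit mean at the same four R values is MSAS 0.19 / 0.14 / 0.11 / 0.06, PROMIS 2.7 / 1.8 / 1.3 / 0.7 and HCV-PRO 6.1 / 4.0 / 2.7 / 1.2.
- Single-visit participants. If a share q enters with its one score, the offset is multiplied by 1 − q. For q = 10% / 30%, PROMIS falls from 4.0 to 3.6 / 2.8 at R = 0.5, and from 2.5 to 2.3 / 1.8 at R = 0.8.
- Skew. Gamma MSAS scores (SD 0.6, assumed mean 0.8) give 0.22 / 0.17 / 0.14 / 0.10 at correlations 0.47 / 0.68 / 0.78 / 0.89.

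**6. The planned covariate model.** The section 15.5 model was simulated with no mean shift, the printed regimen sizes, correlations with T1 assumed 0.50, and 1,500 replicates. Adjusted mean change was 0.40 / 0.31 / 0.25 / 0.18 SD in all five regimens, which matches step 4. The nominal 95% interval at N = 80 excluded zero in 99% / 92–93% / 77–80% / 44–47% of replicates. At N = 960 it did so in 100%.

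**The case against.** The strongest reply is that a worst on-treatment score is a sound measure of peak burden. If symptoms really fluctuate on treatment, a patient's peak really is higher, and visit means can dilute side effects that peak at different times. That stands for MSAS and PROMIS. It does not justify reading the peak against zero or against the important difference when baseline is a single score, and for HCV-PRO the rule gives the best score.

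The size depends on an unknown R. At the lowest planned PROMIS SD of 6, the offset is 2.4 / 1.9 / 1.5 / 1.1, below 3 throughout. This limits the size, not the sign.

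The offset can be lost in wide intervals. It exceeds the N = 80 half-widths only below R of about 0.82. Section 15.12 makes the primary tests specific to cirrhosis subgroups, with cells as small as 40. The step 1 formula then gives half-widths of about 0.21 / 3.5 / 9.0, exceeded only below R of about 0.62. In the largest cells (480) they are about 0.06 / 0.92 / 2.4, and the offset exceeds them even at R = 0.9.

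The offset cancels in comparisons between regimens if SD and R are equal. Such comparisons are auxiliary here, and T3 timing varies with treatment duration, so equal R is not assured.

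The visit-specific means in section 15.3 would help reveal the offset, but they are descriptive and supportive. Section 15.1 promises "guidelines for sensitivity analyses performed to assess the robustness of the major results to reasonable perturbations", without naming one for this problem. It is also fair that section 15.3's statement about increments sits in a supportive section. Section 15.12 and the appendix test of zero mean change carry the point without it.

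**Conclusion.** The concern holds. The HCV-PRO rule contradicts the scale's direction and the purpose of Aim 1, and this needs no assumption about correlation. A 10-point mean loss at one visit alone has expected change of zero or above, and a 10-point loss at both appears as +0.3 to −5.4 for R from 0.5 to 0.9.

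For MSAS and PROMIS, a positive expected change with unchanged visit means follows from the identity for any R below 1. Its size rests on normal scores, equal visit means (the largest case), both visits observed, the appendix central SDs and an assumed R. On those terms MSAS is above its important difference up to R of about 0.91 and PROMIS up to about 0.72. HIT cannot be sized, because the documents give neither an SD nor an important difference for it.

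**What to change.** In section 15.5, for Aims 1a to 1c:

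1. Base the mean changes that are read against zero or the important difference on T1-to-T2 and T1-to-T3, estimated together in one repeated-measures model with the covariates already listed. With no shift, each has expectation zero.
2. Keep the worst on-treatment score, if wanted, as a labelled peak-burden outcome: the larger score for MSAS, PROMIS and HIT, the smaller for HCV-PRO. Do not test it against zero or read it against the important difference. Changing the word for HCV-PRO alone is not enough: with no shift and R = 0.5, the smaller score has expected change −10.3.
3. State how a participant with only one of T2 and T3 enters the peak-burden outcome. Section 15.5 has no rule, and section 15.11 leaves missing PROs to be handled by cause.
4. State whether the Aim 1b rule, worded for T-scores, covers HIT.

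The cost is SAP wording and one refitted model per PRO; T1, T2 and T3 are already collected. The drawback is two mean-change estimates per PRO instead of one, with T3 falling anywhere from weeks 7–8 to weeks 22–24 depending on treatment duration (section 10).

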Nine U.S. liver centers will collaborate to conduct PROP UP. Approximately 1920 patients diagnosed with chronic HCV will be consented and will complete baseline PRO assessments. Patients who are 21 years of age, infected with chronic HCV, and prescribed one of several direct-acting antiviral (DAA) treatment regimens for chronic HCV will be recruited. We anticipate that approximately 15%-20% of the 1920 patients who are consented will not commence HCV therapy, primarily due to insurance denials. Therefore we intend to enroll 1600 patients into longitudinal data collection. Enrollment criteria will include informed consent, completion of baseline PRO surveys, and administration of one dose of a prescribed regimen. These 1600 participants will be followed up to 1 year after HCV treatment ends. Participants will complete several PRO surveys at the following 5 assessment periods: (T1) Baseline, (T2) week 4 on-treatment, (T3) last 2 weeks on-treatment, (T4) 3 months post-treatment, and (T5) 12 months post-treatment for a total study duration of up to 20 months. PRO survey data will be collected via 3 options, selected by each participant: personal technology (home computer, tablet, smartphone) into web-based data capture system; phone-administered surveys with the UNC Call Center; or as a last resort, computer at regular clinic visits. PROs surveys are designed to measure HCV-associated symptoms, pre-existing conditions, treatment side effects, functional status, medication adherence, and out of pocket costs.

Longitudinal data collection of multiple novel PROs before, during and after treatment for HCV are being collected to better understand a variety of issues that are important to patients, clinicians, and stakeholders. Specifically, we will evaluate: (a) prevalence of pre-existing baseline symptoms associated with HCV; (b) the development of new onset treatment side effects and exacerbation of pre-existing symptoms during HCV treatment; (c) medication adherence and out of pocket costs related to HCV treatment; (d) changes in HCV-associated symptoms and functional status in patients who are cured; and (e) long-term patient-reported harms associated with treatments and long-term benefits associated with viral cure.

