These exciting, newly-approved regimens have not been extensively evaluated, particularly with regard to issues that patients care about or longer-term harms and benefits. Differences between specific subgroups of patients have also not been evaluated. Although cure rates are relatively high and side effects fewer and less severe than prior interferon regimens, treatment side effects still exist and may be different between regimens, especially in vulnerable subgroups (e.g., those with cirrhosis, mental health or substance abuse issues). Moreover, the only treatment harms measured in previous trials were captured as clinician-reported adverse events (AEs), as opposed to patient reported. Fatigue, headache, nausea, insomnia, body weakness, diarrhea and rash were reported as AEs in >10% of participants in previous drug trials. Previous research demonstrates that clinician-reported AEs often underestimate the patients’ experience of side effects. Since most symptoms and side effects are a highly subjective, personal experience, the correlation between clinician-reported and patient-reported side effects is often quite low. Finally, patients care about long-term benefits of being cured and whether symptoms associated with HCV attenuate, but few studies address these patient-centered outcomes. Therefore, outcomes chosen by, and reported by patients with the disease, are needed.

Currently, major evidence gaps exist that significantly limit our understanding of the short-term and long-term harms and benefits of these new treatments and thus, patients and clinicians ability to make informed treatment decisions. Patient-centered outcomes research (PCOR) studies are needed to ensure that patients and clinicians understand all of the short term and long-term harms and benefits of these new regimens. The only data currently

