#### 14.2.1 PROMIS short forms to measure HCV-associated symptoms

- PROMIS Fatigue -7a
- PROMIS Sleep Disturbance-8a
- PROMIS General Cognitive Concerns-8a
- PROMIS Pain Interference-8a
- PROMIS Belly/Liver Pain-6
- PROMIS Nausea/vomiting-4
- PROMIS Diarrhea-6
- PROMIS Irritability-5a
- PROMIS Depression-8a
- PROMIS Anxiety-4a

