#### 14.2.2 PROMIS short forms to measure treatment side effects

- PROMIS Fatigue -7a
- PROMIS Sleep Disturbance-8a
- PROMIS Nausea/vomiting-4
- PROMIS Diarrhea-6
- PROMIS Irritability-5a
- PROMIS Anxiety-4a

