## 15.7 Overview of Plans for Manuscript #3: Benefits of Achieving SVR

In the combined convenience sample of participants who achieve SVR (estimated to be ~1500), subgroups defined by achievement of SVR will be characterized and compared in terms of changes in PRO measures. The primary analyses for manuscript #3 will rely on a linear model for change from baseline for each PRO variable conditional on covariates which include *SVR status, cirrhosis status, age, race, sex at birth, treatment regimen, subgroup-by-regimen interaction, cirrhosis-by-regimen interaction, and the baseline PRO score*. Including the baseline PRO score as a covariate has several advantages for clarity of interpretation and improved precision of estimators of interest. The analysis will focus on point estimates and confidence intervals. PRO variables of interest in manuscript #3 are described here by aim:

Aim 3a1, MSAS. The outcome variable will be change from baseline (T1) to 3 months after end of treatment (T4). As an aid to interpretation, additional supportive tabulations for each of the 32 symptoms will be examined; e.g., change in side effects or pre-existing symptoms will be characterized in regard to change in raw frequency, severity and distress items.

Aim 3a2, PROMIS®. The primary analyses will focus on 10 symptom-specific PROMIS® T-scores and 1 HIT headache score. The outcome variable will be change from baseline (T1) to 3 months after end of treatment (T4). As an aid to interpretation of the main results, additional supportive tabulations for specific survey items will be examined.

Aim 3b, HCV-PRO. In the primary analysis, the outcome variable will be change from baseline (T1) to 3 months after end of treatment to determine benefit to well-being and functioning after cure (T4).

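### Depression, Cognitive Concerns, Pain Interference and Belly Pain are measured on treatment but have no committed baseline-adjusted estimate of on-treatment change by regimen in Manuscript #1.

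*Combined protocol and SAP*

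**What the plan says.** For Manuscript #1, section 15.5 (Aim 1b) states: "The primary analyses will focus on 6 side effect-specific PROMIS® T-scores and 1 HIT headache score". It defines the outcome as follows: "The outcome variable will be change from baseline (T1) to the larger of the two T-scores (T2 and T3) during treatment". The model adjusts for the baseline score and includes regimen, cirrhosis status and their interaction. The six scales are those that section 14.2.2 lists as side-effect measures.

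Section 14.2.1 lists ten PROMIS forms as measures of HCV-associated symptoms, and Table 4 (section 11.4) schedules all ten at every assessment from T1 to T5. For change to T4, section 15.7 says: "The primary analyses will focus on 10 symptom-specific PROMIS® T-scores and 1 HIT headache score". Section 15.8 uses the same set for change to T5.

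The Brief Summary names among the study's targets "the development of new onset treatment side effects and exacerbation of pre-existing symptoms during HCV treatment". Aim 1 in section 3.1 is to characterise the harms of each regimen from baseline to T2 and T3.

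**The concern.** The plan treats depression, cognitive difficulty, pain and belly pain as symptoms of HCV, and it undertakes to look at worsening of existing symptoms during treatment. It collects a dedicated scale for each at both on-treatment visits. The manuscript that reports on-treatment harm then fits its regimen-level model to the other six scales only, and the documents give no reason for the split.

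If a regimen produced a temporary rise on one of these four scales, a reader of Manuscript #1 would find no adjusted PROMIS estimate of it for that regimen. The domains matter to patients whom the Introduction singles out: it expects that side effects may differ between regimens, "especially in vulnerable subgroups (e.g., those with cirrhosis, mental health or substance abuse issues"). Section 15.12 expects about half the sample to have a mental-health or substance-abuse history.

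**Working it through.** **1. Which scales are affected.** The section 14.2.1 list has ten forms and the section 14.2.2 list has six, all of them also among the ten. The difference is exactly four: Depression, Cognitive Concerns, Pain Interference and Belly/Liver Pain.

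| Scales | Collected at T2 and T3 (Table 4) | Modelled on treatment (15.5) | Modelled at T4 (15.7) | Modelled at T5 (15.8) |
|---|---|---|---|---|
| Six side-effect scales | yes | yes | yes | yes |
| The four others | yes | no | yes | yes |

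**2. What else covers the four on treatment.**
- Section 15.3 commits to descriptive trajectory summaries, with means at each occasion and confidence intervals. It states no baseline adjustment or regimen breakdown and does not assign them to Manuscript #1. Longitudinal modelling of the symptom scores is left optional.
- Aim 1a models the total MSAS score. Individual symptoms receive supportive tabulations, which include worsening of existing symptoms. The documents do not list the 32 items, so overlap with the four scales can be neither confirmed nor excluded.
- Aim 1c models the HCV-PRO, which includes physical and emotional functioning. A higher HCV-PRO score is better (section 14.4), yet section 15.5 takes the larger of the T2 and T3 scores, which is the more favourable one. It is a weak check on worsening.

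**3. What the later contrasts can show.** Take a patient with score b at T1, b + 3 on treatment and b again at T4 and T5. The on-treatment change is +3. The T1-to-T4 change is b − b = 0, and so is the T1-to-T5 change. The episode appears in neither contrast.

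**4. Precision if the four scales are added.** Inputs from the Appendix: SD = 10 (range 6 to 12), serial correlation R = 0.50, important difference 3 points. The SD of change is 10 × √(2 × (1 − 0.5)) = 10. The half-width met with 80% probability is

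h = t(0.975, n−1) × 10/√n × √(χ²₀.₈₀(n−1)/(n−1)).

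| n | computed | plan |
|---|---|---|
| 80 | 2.367 | 2.37 |
| 160 | 1.632 | 1.63 |
| 960 | 0.645 | 0.65 |

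The plan's figures are reproduced. At N = 80 its range over SD 6 to 12 is 1.42 to 2.84, still below 3.

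**5. Precision if split by mental-health or substance-abuse history.** Table 6 gives 40 per subgroup in the two smallest cohorts (Viekira Pak and daclatasvir/sofosbuvir). Then h = 2.023 × 1.581 × 1.088 = 3.48, above 3. Over SD 6 to 12 this scales to 3.48 × 0.6 = 2.09 and 3.48 × 1.2 = 4.18. Pooled across regimens, with about 800 per group, h is about 0.71.

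**6. Multiplicity, as a side remark.** Manuscript #1 would go from 7 to 11 PROMIS and HIT outcomes. If each were tested at 0.05 and the tests were independent (an assumption), the chance of at least one false positive would rise from 1 − 0.95⁷ = 0.30 to 1 − 0.95¹¹ = 0.43. Section 15.5 centres on estimates and intervals, so this argues for a secondary label and not against the addition.

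**The case against.** The selection is prespecified and agrees with section 14.2.2. Which scales are primary is a design choice, and the wording of Aim 1b sets a focus without forbidding other analyses. Worsening of existing symptoms is not ignored either, since the MSAS tabulations address it directly. All of this stands, and it limits the point to an unexplained gap in the modelled outcomes.

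Two things keep that gap open. Section 14.2 justifies the PROMIS forms by their precision on specific constructs, unmixed with other symptoms, so tabulated MSAS items are not an equal substitute. The split is also not carried through: Aim 4b in section 3.1 describes the one-year PROMIS results as long-term side effects, and section 15.8 carries it out with all ten scales.

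A reader might infer that the four scales have no on-treatment analysis at all. The documents do not support that, because section 15.3 commits to descriptive trajectories with intervals. A reader might also infer that the benefit report would credit recovery from treatment-induced worsening as an advantage of cure. It would not: Manuscript #3 compares T4 with T1, so a return to baseline counts as zero. The T4 and T5 models estimate change in either direction, and Manuscript #4 covers harms as well as benefits.

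**Conclusion.** The point holds as a cheap improvement. Four of the ten PROMIS scales measured on treatment lack a committed, baseline-adjusted, regimen-specific estimate of on-treatment change, and a worsening that resolves before T4 would not be seen in the later contrasts. Whether any regimen causes such worsening cannot be judged from the documents, so the consequence is missing information and not a demonstrated bias. No sample-size figure is wrong.

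The statement that the added estimates would be precise enough rests on the plan's SD and correlation, complete data, and change to a single time point. The Aim 1b outcome is the larger of two scores, so its SD may differ from 10. The same limitation applies to the six scales already planned.

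**What to change.** In section 15.5, Aim 1b, keep the six side-effect scales plus HIT as the primary set. Add Depression, Cognitive Concerns, Pain Interference and Belly Pain as a named secondary set, for example *exacerbation of pre-existing symptoms*, using the same baseline-adjusted change model. Report point estimates and confidence intervals by regimen. If the sponsor prefers to leave the four out, the section should say why.

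The documents do not state the scoring direction of each PROMIS form. Confirm that a higher T-score means worse on each of the four before applying the larger-of-two rule. Because the larger of two noisy scores tends to exceed a single one even without true change, show the T2 and T3 means beside the modelled result.

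Any breakdown by mental-health or substance-abuse history should be pooled across regimens. It needs a term that the section 15.5 model does not contain, and it should not be crossed with the smallest cohorts.

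The cost is a few lines of text, four more runs of a planned model, and four more intervals per regimen, labelled secondary. No new data or participants are needed. The history term, if wanted, is a small extra modelling step.
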